## 7.1 Lipid Profile/Biomarkers

Samples will be collected for the lipid profile/biomarkers at visits specified in the Schedule of Procedures (Appendix A). The lipid profile/biomarker samples will be analyzed for ApoB, HDL-C, LDL-C, non-HDL-C, TC, and TG. Samples should be collected while the participant is fasting (a minimum of 8 hours).

At Baseline (Visit 2), Day 84 (Visit 4), and Day 365 (Visit 7)/EOT/ET, LDL-C will be measured for all participants by preparative ultracentrifugation, also referred to as beta quantification. At all other scheduled visits, LDL-C will be calculated using the Friedewald equation unless TG  $\geq$ 400 mg/dL ( $\geq$ 4.5 mmol/L) or LDL-C  $\leq$ 50 mg/dL ( $\leq$ 1.3 mmol/L). If TG  $\geq$ 400 mg/dL ( $\leq$ 4.5 mmol/L) or LDL-C  $\leq$ 50 mg/dL ( $\leq$ 1.3 mmol/L), then LDL-C level will be measured directly by preparative ultracentrifugation.

All lipid profile/biomarker values will be blinded during the study through the EOS Visit (Visit 8). Participants, the Sponsor, Investigators, and all study site personnel involved in the study, including personnel carrying out study procedures, evaluating participants, entering study data, and/or evaluating study data, will remain blinded to lipid profile/biomarker values until all participants have completed the EOS Visit and the database has been locked for analysis.

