3.1.4 Definition of Baseline

Baseline is defined as the last measurement prior to the first dose of study drug, unless otherwise stated.

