Supplemental analyses will be performed for the primary efficacy endpoint in order to assess any differences with the results from the primary analysis and investigate what effect, if any, protocol violations have on the trial results. In the first supplemental analysis, a mixed model for repeated measures (MMRM) approach will be utilized. The LDL-C values measured by preparative ultracentrifugation will be used. The analysis will include fixed effects for treatment group, visit, and treatment-by-visit interaction, along with covariates of the Baseline LDL-C value as a continuous covariate, CV risk (HeFH or non-HeFH), Baseline statin therapy (HIS or non-HIS). The restricted maximum likelihood estimation approach will be used with an unstructured covariance matrix. The LS mean, standard errors, and 2-sided 95% confidence intervals for the treatment group and for the comparison of the treatment group to the placebo group will be provided. The MMRM approach will include all available assessments of percent change in LDL-C from Day 1, Day 30, Day 84, Day 180, Day 270, and Day 365. The model assumes that the data are missing at random (MAR). If any data are missing, the model will use all information from the other time points to estimate the mean treatment difference at the given time point. No imputation of missing data will be performed. The analysis will be conducted for ITT Population.

The analysis will be implemented using SAS® Proc Mixed. The sample SAS code can be found below:

Note:

USUBJID = unique subject identifier
TREATMENT = 0 (Placebo), 1 (Obicetrapib)
VISIT = visit
LDLC_BASE = Baseline LDL_C value
PCHG = Percent change from Baseline
CVRISK = 1 (HeFH), 0 (non-HeFH)
STATIN = 1 (HIS), 0 (non-HIS)

```
proc mixed;
  class USUBJID TREATMENT VISIT CVRISK STATIN;
  model PCHG = TREATMENT LDLC_BASE CVRISK STATIN VISIT TREATMENT*VISIT / solution cl;
  Repeated VISIT / TYPE=UN sub=USUBJID;
  lsmeans VISIT*TREATMENT / cl diff;
```

run;

Additional supplementary analysis will be performed using the ANCOVA model from the primary analysis based on the FAS, MITT, MITT On Treatment, and PP populations. No imputation for missing data will be performed for the analysis.

Secondary Estimand

A secondary estimand will be assessed for the primary efficacy endpoint. The secondary estimand is defined by the following key attributes:

- **Treatment:** obicetrapib versus placebo
- **Target Population:** participants who are randomized into the study

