- **Analysis Population:** The ITT Population
- **Intercurrent events:** treatment discontinuation, prohibited medication use
- **Analysis set and handling of intercurrent events:** A hypothetical strategy will be used. All available values of LDL-C at Baseline and Day 84 will be included in the calculation of the percentage change from Baseline to Day 84.
- **Population level summary:** The difference in LS mean percentage change in LDL-C from Baseline to Day 84 between treatment groups.

This hypothetical estimand represents the treatment effect of obicetrapib relative to placebo at Day 84 in the randomized participants had they remained on their randomized treatment for the entire planned treatment period. This estimand uses a hypothetical strategy to handle intercurrent events and is intended to provide an estimation of the achievable study treatment effect participants take the treatment as planned. The resulting missing values (corresponding to unobserved values or excluded values following study drug discontinuation or the use of prohibited medication) will be implicitly handled by using an MMRM approach under the assumption of missing at random. The model will be similar to the MMRM approach described previously for the supplemental analysis of the primary efficacy endpoint.

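### The MMRM lists Day 1, which is Baseline, as a percent-change response visit; if those zeros are entered, the unstructured REML fit has no maximum

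*SAP*

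**What the plan says.** SAP 3.4.1, Supplemental Analyses, describes an MMRM in the ITT Population whose responses are to "include all available assessments of percent change in LDL-C from Day 1, Day 30, Day 84, Day 180, Day 270" and Day 365. On the covariance it says: "The restricted maximum likelihood estimation approach will be used with an unstructured covariance matrix". The sample code has "model PCHG = TREATMENT LDLC_BASE CVRISK STATIN VISIT TREATMENT*VISIT / solution cl" with TYPE=UN over VISIT. LDLC_BASE, CVRISK and STATIN therefore have one coefficient each, shared by all visits, while treatment-by-visit is free at every visit. VISIT has no further definition, and no statement drops Day 1.

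SAP 3.1.4 says: "Baseline is defined as the last measurement prior to the first dose of study drug". Protocol 7.1 places that measurement: "At Baseline (Visit 2), Day 84 (Visit 4), and Day 365 (Visit 7)/EOT/ET, LDL-C will be measured for all participants by preparative ultracentrifugation". SAP 3.1.2 (Tables 2 and 3) lists Day 1 (Visit 2) as an analysis visit.

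For the hypothetical estimand, SAP 3.4.1, Secondary Estimand, says: "The model will be similar to the MMRM approach described previously for the supplemental analysis of the primary efficacy endpoint". It gives no visit list or code of its own.

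**The concern.** A response that is constant by construction has no variance to estimate. Under an unstructured covariance its variance is a free parameter that can go to zero, which leaves the likelihood unbounded. The covariate coefficients are shared across visits, so exact zeros at Day 1 also pull them to zero at Day 84.

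The SAP names no fallback covariance for this model. If the fit fails, someone must decide after unblinding which visits or which covariance structure to drop. This is the first supplemental analysis, and a similar model is the only estimator stated for the hypothetical estimand, so that choice should be settled beforehand.

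**Working it through.** **Inputs from the documents.** Six listed visits, REML, unstructured covariance and common covariate coefficients (SAP 3.4.1). Baseline is the last pre-dose value, taken at Visit 2 (SAP 3.1.4, Protocol 7.1). Allocation is 2:1 (SAP 2.2.1). There are 2280 evaluable participants, hence 1520 and 760, with a 30-point effect, SD 15 and 5% dropout (SAP 2.2.2). The plan states no figure for this model, so there is none to reproduce.

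**Assumed, not in the documents.** Baseline LDL-C mean 100 and SD 30 mg/dL; within-participant correlation 0.5; 17% HeFH; 70% on high-intensity statins (the SAP gives this only as a minimum); 5% missing at each post-baseline visit; baseline slope of -0.10 or -0.25 points per mg/dL. One data set was simulated per slope.

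**Step 1: the Day 1 response.** Percent change = 100 × (Day 1 value - Baseline)/Baseline. With the Day 1 value as Baseline this is 0. It could differ only if the Visit 2 sample were drawn after the first dose, and a few such cases would not make the model sound.

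**Step 2: the likelihood.** Set the three shared coefficients and the two Day 1 arm means to zero. Every Day 1 residual is then exactly zero. With Day 1 variance v, uncorrelated with the other visits, Day 1 adds n ln(v) to -2 log L and no quadratic term. Under REML this becomes (n - 5) ln(v), because the Day 1 rows determine five parameters. As v goes to 0, -2REML goes to minus infinity. Each hundredfold cut in v should lower it by (2280 - 5) × ln(100) = 2275 × 4.60517 = 10,476.8.

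The numerical profile for slope -0.10 agrees:

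| v | -2REML | Drop |
|---|---|---|
| 1 | 65,921.0 | |
| 0.01 | 55,445.3 | 10,475.7 |
| 0.0001 | 44,968.5 | 10,476.8 |
| 0.000001 | 34,491.7 | 10,476.8 |

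**Step 3: free fit with the zeros entered.** For slope -0.10, -2REML went from 71,618 at the start to -36,876 at iteration 8 and -833,067 at iteration 72. The Day 1 variance fell from 1 to about 2e-172, and the shared baseline coefficient fell to about 1e-87 in size. Slope -0.25 behaved the same way. With Day 1 removed and nothing else changed, the model fitted normally (-2REML 65,742, covariance condition number about 6.5).

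**Step 4: the Day 84 contrast, estimate (SE).**

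| Assumed slope | Day 1 removed, adjusted | Day 1 zeros entered | No covariates |
|---|---|---|---|
| -0.10 | -30.054 (0.684) | -30.240 (0.697) | -30.240 (0.697) |
| -0.25 | -30.054 (0.684) | -30.536 (0.760) | -30.532 (0.761) |

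SE ratios: 0.697/0.684 = 1.02 and 0.760/0.684 = 1.11. The unstructured covariance does not restore the adjustment, because the arm means at Day 1 are free.

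**Step 5: range.** Losing adjustment for a baseline value with correlation r inflates the SE by about 1/√(1 - r²): 1.00 at r = 0, 1.02 at 0.2, 1.05 at 0.3 and 1.15 at 0.5.

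**Step 6: the rest of the visit list.** The same SAP paragraph calls for ultracentrifugation values. Protocol 7.1 and SAP 3.4.2 provide these at Days 30, 180 and 270 only when triglycerides are at least 400 mg/dL or LDL-C is at most 50 mg/dL. Deleting Day 1 alone would leave three visits populated by values selected partly on the outcome.

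**The case against.** The strongest reply is that the sample code names no visits. If percent change is left blank on baseline records, PROC MIXED drops those rows, the same code runs on post-baseline visits only, and the problem disappears. That is correct, so the failure depends on how the analysis data set is built. It does not rescue the text, because the SAP lists Day 1 alongside five response visits and never says its percent change is to be blank.

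The sentence can also be read as naming Day 1 as the reference for change. This is less natural, given the parallel list, and one clause would settle it.

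A third reply is that little depends on this model. That stands. The primary analysis is ANCOVA with multiple imputation, none of the four sensitivity analyses uses the MMRM, and the secondary endpoints are tested with ANCOVA. An unbounded likelihood would more likely appear as a fitting failure than as hidden bias. An unadjusted estimate would still be a randomised comparison, and the conclusion would not change at the planned 30-point effect.

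A reader might also infer that the hypothetical-estimand analysis necessarily has the same fault. The documents do not go that far: its model is described only as similar, with no visit list of its own.

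**Conclusion.** The specification is wrong as written and should be corrected. Entered literally, the Day 1 zeros leave the REML criterion without a maximum. This follows from algebra and does not depend on the simulation assumptions. What is lost if software nevertheless returns an estimate does depend on them: a Day 84 standard error larger by about 0 to 15% for correlations from 0 to 0.5 in size, and about 2% and 11% in the two scenarios fitted. No single figure can be defended, because the documents do not give the correlation. The fits were made outside SAS, so they do not show what PROC MIXED would report.

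Two stronger readings are tempting. One is that the MMRM can never be fitted from this code; it can, if baseline records carry no percent change. The other is that the shared baseline coefficient is itself an error. It does harm here only because of the Day 1 zeros, since the five-visit model with shared coefficients fitted normally.

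The first supplemental analysis is affected, and so is the hypothetical-estimand analysis if its model copies the visit list. The primary analysis and the testing sequence are not.

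**What to change.** In SAP 3.4.1, Supplemental Analyses, restrict the MMRM responses to post-baseline visits and state that Day 1 enters only through LDLC_BASE. State the same under Secondary Estimand. In the sample code, add a restriction on VISIT or a note that percent change is blank on baseline records.

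In the same edit, reconcile the ultracentrifugation-only rule with Protocol 7.1 and SAP 3.4.2. One way is to apply the SAP 3.4.2 LDL-C rule at Days 30, 180 and 270 and keep ultracentrifugation at Days 84 and 365.

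An LDLC_BASE-by-VISIT term is an optional refinement. On its own it would not cure the problem, because the Day 1 variance would still be zero.

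The cost is a few sentences, one line of code and a decision on the LDL-C method at three visits. No data collection or sample size changes.

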#### 4.3 Withdrawal Criteria

Participation of a participant in this clinical study will be discontinued for any of the following reasons:

- Withdrawal of consent; or
- Termination of the study by the Sponsor or the regulatory authority.

Study drug treatment may be discontinued either permanently or temporarily (although the participant should be encouraged to remain in the study and to follow-up for study visits) for any of the following reasons:

- Occurrence of any medical condition or circumstance that exposes the participant to substantial risk and/or does not allow the participant to adhere to the requirements of the protocol;
- Any serious AE (SAE), clinically significant AE, severe laboratory abnormality, intercurrent illness, or other medical condition which indicates to the Investigator that continued participation is not in the best interest of the participant;
- Pregnancy (permanent discontinuation of study drug);

- Requirement of prohibited concomitant medication; or
- Participant failure to comply with protocol requirements or study-related procedures.

Participants are free to withdraw consent from the study (which means permanent discontinuation of study drug and all follow-up assessments) at any time without prejudice. Note that discontinuation of study drug in and of itself is **not** considered withdrawal of consent.

An excessive rate of withdrawals (either discontinuation of study drug or study withdrawal) can render the study non-interpretable. Therefore, unnecessary withdrawal of participants should be avoided, and all efforts should be taken to motivate participants to comply with all of the study-specific procedures and to continue follow-up until the end of the study to detect the occurrence of CV events and assess vital status.

Every attempt should be made to keep participants on study drug throughout the duration of the study. Before permanently discontinuing study drug (either participant- or Investigator-initiated), an interruption should be considered. Participants who temporarily discontinue study drug for any reason should restart as soon as it is medically justified in the opinion of the Investigator. In addition, participants should not be withdrawn from the study drug or from the study after experiencing a potential CV event.

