All participants who permanently discontinue study drug should continue scheduled study visits. If the participant declines continued onsite visits but is agreeable to telephone calls, he/she will be contacted by the Investigator periodically to assess occurrence of CV events until death, documented withdrawal of participant informed consent (in writing if allowed by local regulations), or the final closure of the study.

The Investigator should show due diligence and explore all possible options to reach a participant who fails to return for a visit. In the case of participants lost to follow-up, attempts to contact the participant must be made and documented in the participant's medical records and in source documents. Per routine, in order to avoid participants lost to follow-up, the Investigator should ask the participant at the study start for the contact details of a relative or friend who can be contacted for participant contact information in case the participant cannot be reached.

Participants should not be withdrawn from follow-up unless they explicitly withdraw consent to be contacted. All efforts should therefore be made to minimize the number of participants who withdraw consent as, in general, no further information on CV events and survival status may be collected after that point. Participants who do not want regular in-person follow-up after cessation of study drug should be offered alternative methods of follow-up, including periodic telephone follow-up, contact at study closure, or assessment of health status via treating physicians or medical records. Such participants would then not be viewed as withdrawal of consent. The Investigator must explain to the participant all options for continued participation, and document which options were refused by the participant and the reason for refusal. Withdrawal of consent to all follow-up must be ascertained and documented in writing by the Investigator, who must inform the Sponsor and document the withdrawal of consent in the eCRF and medical records.

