## 9.2.1 Analysis of Efficacy

## 9.2.1.1 Primary efficacy analysis

The ITT Population will be the primary population for the efficacy analysis. Efficacy will also be analyzed using the FAS, mITT Population, and PP Population as supplementary analyses.

The primary efficacy endpoint is the percent change from Baseline to Day 84 in LDL-C in the obicetrapib group compared to the placebo group. The primary endpoint will be analyzed using an analysis of covariance (ANCOVA) model with a fixed effect for the treatment group and covariates of Baseline LDL-C, CV risk (HeFH or non-HeFH), and Baseline statin therapy (HIS or non-HIS). The least squares (LS) mean, standard errors, and 2-sided 95% confidence intervals for each treatment group and for the mean difference compared to placebo will be obtained. The model will be fit assuming unequal variances for each treatment group.

The primary estimand will correspond to a treatment policy estimand. The target population will comprise participants who are randomized into the study. The primary summary measure to assess the treatment effect will be the LS mean difference for the primary endpoint between obicetrapib

and placebo based on the ANCOVA methodology. The primary estimand will be addressed using the in-study observation period (ie, including data collected post-treatment discontinuation or post-prohibited medication use).

Missing data will be imputed for the primary efficacy analysis based on a pattern mixture model that uses a multiple imputation technique analyzed with ANCOVA with pre-specified fixed factors and covariates. If appropriate, based on the number of retrieved dropouts, missing measurements of non-retrieved dropouts will be modeled by known measurements from retrieved dropouts (ie, participants who remain in the study after treatment discontinuation) in the same treatment group. The imputation model will be further clarified in the SAP.

Additional sensitivity analyses may be carried out under secondary estimands and/or various assumptions for missing data. Full details will be provided in the SAP.

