3.4.1 Primary Efficacy Endpoints

Primary Analysis

The primary efficacy endpoint is the percentage change from Baseline to Day 84 in LDL-C in the obicetrapib group compared to placebo group.

The LDL-C values measured by preparative ultracentrifugation (PUC) will be used. If the later is not available, the LDL-C values will be assumed missing.

All the analysis for primary efficacy endpoint will be repeated with LDL-C values calculated as follows:

1. LDL-C will be calculated using the Friedewald equation unless triglycerides ≥ 400 mg/dL or LDL-C ≤ 50 mg/dL; where, LDL-C level will be measured directly by PUC.
2. LDL-C will be calculated using the Martin-Hopkins equation unless triglycerides ≥ 400 mg/dL or LDL-C ≤ 50 mg/dL; where, LDL-C level will be measured directly by PUC.

Primary Estimand

To assess the primary efficacy endpoint, the primary estimand is defined by the following key attributes:

- **Treatment:** obicetrapib versus placebo
- **Target Population:** participants who are randomized into the study
- **Analysis Population:** The ITT Population
- **Intercurrent events:** treatment discontinuation, prohibited medication use
- **Analysis set and handling of intercurrent events:** Treatment policy strategy will be used. All available values of LDL-C at Baseline and Day 84 will be included in the calculation of the percentage change from Baseline to Day 84.
- **Population level summary:** The difference in LS mean percentage change in LDL-C from Baseline to Day 84 between treatment groups

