Missing data at Day 84 will be imputed using a retrieved dropout imputation model assuming the data are missing not at random (MNAR). At Day 84, the data will be split into two groups as follows: (1) all participants that did not discontinue treatment and had a non-missing value at Day 84; and (2) either participants that had a missing value at Day 84, or participants that had discontinued treatment and had a non-missing value at Day 84. For the second group, 100 data sets will be imputed. The variables for the imputation model will consist of the LDL-C values from Baseline and Day 84, along with treatment group, CV risk (HeFH or non-HeFH) and Baseline statin therapy (HIS or non-HIS). Each data set will be combined with the first group to obtain 100 imputed data sets with no missing values at Day 84. For each imputation data set, the percent change from baseline to Day 84 will be analyzed using the ANCOVA model described above. The results of these 100 analyses will be combined to construct the treatment estimates using the parameter estimates and associated standard errors. Similarly, the difference of the adjusted treatment means (obicetrapib vs. placebo) will be presented with the associated standard error and two-sided 95% confidence interval. Randomly chosen seed numbers will be selected for the analysis and will be retained.

Sample SAS code is shown below:

1.1

```
*****
Note: Missing value imputation only using participant group (2): participants that had a
missing value at Day 84, or participants that had discontinued treatment and had a non-
missing value at Day 84
```

TREATMENT = 0 (Placebo), 1 (Obicetrapib)

LDLC_BASE = Baseline LDL_C value

LDLC_Day84 = LDL_C value at Day 84

CVRISK = 1 (HeFH), 0 (non-HeFH)

STATIN = 1 (HIS), 0 (non-HIS)

```
*****
proc mi data=LDL_C seed=8267356 n impute=100 out= LDL_C_IMP;
class TREATMENT CVRISK STATIN;
monotone method=reg;
var TREATMENT CVRISK STATIN LDLC_BASE LDLC_DAY84;
run;
```

1.2

```
*****
Note: LDL_C_IMP dataset must be merged with dataset containing participants from
group (1): participants that did not discontinue treatment and had a non-missing value at
Day 84.
```

Note: For each imputation dataset, the percentage change from Baseline to Day 84 will be analyzed using an ANCOVA approach with a fixed effect for the treatment group and covariates of Baseline LDL-C, CV risk (HeFH or non-HeFH), and Baseline statin therapy (HIS or non-HIS).

TREATMENT = 0 (Placebo), 1 (Obicetrapib)

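### SAP 3.4.1: the hypothetical secondary estimand carries the treatment-policy data rule and so contradicts its own exclusion clause (minor, secondary estimand only)

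*SAP*

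**What the plan says.** SAP 3.4.1 defines two estimands for the Day 84 LDL-C endpoint. Both name the same intercurrent events, treatment discontinuation and prohibited medication use.

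- **Primary estimand, handling attribute:** "Treatment policy strategy will be used. All available values of LDL-C at Baseline and Day 84 will be included". Protocol 9.2.1.1 ties this rule to the primary estimand, which uses the in-study observation period, "including data collected post-treatment discontinuation or post-prohibited medication use".
- **Secondary estimand, handling attribute:** "A hypothetical strategy will be used. All available values of LDL-C at Baseline and Day 84 will be included in the calculation".
- **Secondary estimand, narrative below the list:** the target is the effect if participants had stayed on their assigned treatment. The missing values passed to the MMRM, under missing at random, include "excluded values following study drug discontinuation or the use of prohibited medication".
- **Model referred to:** the narrative says the MMRM will be similar to that of the first supplemental analysis, whose data rule is: "The MMRM approach will include all available assessments of percent change in LDL-C".

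**The concern.** The handling attribute is the part of the definition that should separate the two estimands. Here the strategy label changes but the data rule does not. A Day 84 value observed after an intercurrent event is kept by the attribute and removed by the narrative. The cross-reference to the supplemental MMRM does not settle the matter, because that model also takes every available assessment. Its sample code shows no exclusion step, and no separate code is given for the secondary estimand.

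The secondary estimand is there to show the Day 84 effect under continued treatment, next to the treatment-policy result. A programmer who followed the attribute and the supplemental data rule would essentially reproduce the first supplemental MMRM under a hypothetical label. Readers comparing the two estimands would then believe that the data rules differ when they do not.

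**Working it through.** **1. Do the rules conflict on real values?** Yes. Protocol 4.3 states: "All participants who permanently discontinue study drug should continue scheduled study visits". The primary imputation in SAP 3.4.1 defines a group that includes "participants that had discontinued treatment and had a non-missing value at Day 84". Day 84 values after stopping drug are therefore expected to exist.

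**2. The plan's own figure.** Inputs from SAP 2.2.2 and 2.2.1: 2400 randomised 2:1, 5% dropout, a 30-point reduction, SD 15, one-sided alpha 0.025.

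- Evaluable: 2400 × 0.95 = 2280, which is 1520 obicetrapib and 760 placebo.
- SE of the difference: 15 × √(1/1520 + 1/760) = 0.666.
- Ratio of effect to SE: 30 / 0.666 ≈ 45, so power is about 1.00. This agrees with the stated power of more than 90%, and the present point does not change it.

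**3. Illustrative dilution from obicetrapib participants who stop drug.** The documents give no share of participants who are off drug with a Day 84 value. Assumptions: a share p of 1% to 2% of the obicetrapib arm (about 15 to 30 of 1520); a fraction r of the effect remaining, 0 or 0.5; and an on-treatment effect equal to the plan's 30 points.

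Dilution = p × 30 × (1 − r)

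| p | r | Dilution (points) | In SEs | Estimated reduction |
|---|---|---|---|---|
| 0.01 | 0.5 | 0.15 | 0.23 | 29.85 |
| 0.01 | 0 | 0.30 | 0.45 | 29.70 |
| 0.02 | 0.5 | 0.30 | 0.45 | 29.70 |
| 0.02 | 0 | 0.60 | 0.90 | 29.40 |

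**4. Prohibited medication.** Extra lipid-lowering therapy in the obicetrapib arm would enlarge the apparent effect; in the placebo arm it would shrink it. Protocol 8.8.4 allows such intensification after a confirmed critical LDL-C value or high triglycerides. Before Day 84 the LDL-C alert in Protocol 8.8.3 needs both a value above 200 mg/dL and a rise of more than 50%, so this route is probably rare. The net direction cannot be derived from the documents.

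**5. Precision cost of applying the exclusion.** With share p set to missing in both arms, SE = 0.666 / √(1 − p).

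- p = 0.01: 0.670 (+0.5%)
- p = 0.02: 0.673 (+1.0%)

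Other visits in the MMRM would recover almost none of this. The supplemental MMRM uses ultracentrifugation values. Under Protocol 7.1 and SAP 3.4.2 these are routine only at Baseline, Day 84 and Day 365 (or the end-of-treatment or early termination visit). At Days 30, 180 and 270 they are taken only when triglycerides are at least 400 mg/dL or LDL-C is at most 50 mg/dL. Someone who stops before Day 84 would usually have no on-drug post-baseline value of this kind.

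**The case against.** The strongest reply is that the section resolves itself. The label says hypothetical, the target is the effect under continued treatment, and the exclusion is written into the narrative. One can also read the attribute in two steps: percent change is first calculated from whatever is available, then values after an intercurrent event are dropped before modelling. In addition, Protocol 9.2.1.1 makes analyses under secondary estimands optional, and nothing in the testing sequence of SAP 3.4.2 depends on this one.

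Much of this stands. It settles the intent and keeps the point minor. It does not rescue the sentence. The same words serve in the primary estimand to keep values after an intercurrent event, nothing in the secondary estimand qualifies them, and the exclusion appears only inside a parenthesis.

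The size is also open to challenge, because the assumed shares have no source. The shift is linear in the share: with no remaining effect it would be 1.5 points at 5% and 3.0 points at 10%. The plan's 5% dropout figure does not supply the share, since it concerns participants who are not evaluable. The documents also do not say whether the planned 30 points is an on-treatment effect.

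A reader might infer that the sponsor intends to keep off-drug values, or that the reported hypothetical effect is bound to be too small. The documents support neither. The narrative points to exclusion, and dilution is shown only for stopping obicetrapib, not for prohibited medication.

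**Conclusion.** The attribute's data sentence is wrong as written and contradicts the exclusion stated in the same definition. The severity is minor and confined to the secondary estimand of the primary endpoint. If the sentence were followed, the dilution from obicetrapib discontinuation would be below one standard error at the assumed shares of 1% to 2%; this is an illustration and not an estimate. A reader might go further and infer that the primary result is compromised. It is not: keeping all values is right under treatment policy, and the primary estimand, sample size and testing order do not rely on this sentence.

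**What to change.** In SAP 3.4.1, Secondary Estimand, replace the attribute's data sentence with: *LDL-C values collected after permanent study drug discontinuation, while off drug during a temporary interruption, or after the start of prohibited medication are set to missing at every post-baseline visit before the MMRM is fitted; values after study drug is restarted are kept.* Add: *The rule in the first supplemental analysis that all available assessments are used does not apply to this estimand.*

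Two parts of this wording are clarifications added to the SAP's own exclusion clause. The all-visits scope is needed because the MMRM models the visits jointly. The restart rule is needed because Protocol 4.3 says "Study drug treatment may be discontinued either permanently or temporarily" and asks those who pause to restart when medically justified. Blanking every visit after any pause would discard on-drug values that this estimand should keep.

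The cost is two sentences before database lock. If lock has passed, SAP section 1 provides for documenting the deviation in the Clinical Study Report. No protocol amendment, new data or change to the primary estimand, primary analysis or testing order is needed. The downside is the negligible loss of precision shown in the working.
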